6.2 Drug administration

The patients will self administer peg-IFN injections subcutaneously. They will be taught how to perform the injection by research nurses or clinical nurse specialists on their first dose. Nurses will also explain where it is suitable to inject.

6.3 Dose Modifications for Toxicity

If neutrophil counts fall below 1×10^9 /ml or platelets fall below 100×10^9 /ml the dose of Peg-IFN will be reduced to 90 mcg / week. If the neutrophil count falls below 0.5 10^9 /ml or the platelet count falls below 50 10^9 /ml then Peg-IFN will be discontinued until the counts recover.

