4 PARTICIPANT ENTRY

4.1 Study population

Subjects for the trial will be recruited from hepatology or hepatitis specialist clinics where appropriate patients are already being monitored on treatment with nucleos(t)ide analogues. By definition these patients are strongly adherent with clinic appointments and antiviral drugs. Patients will be given a patient information sheet and invited to an appointment at least one week later.

The trial will be open to patients with HBeAg negative chronic HBV infection who have been treated with nucleos(t)ide analogues for a minimum of three years with HBV DNA < 400 IU/ml for a minimum of two years. After screening all patients will be monitored for 4 - 12 weeks to confirm they continue to meet the inclusion criteria as listed below.

(i) Inclusion criteria

- Age ≥ 18
- Chronic HBV infection
- HBeAg negative
- Nucleos(t)ide analogues treatment for ≥3 years
- HBV DNA < 400 IU/mI ≥2 years
- Informed consent

(ii) Exclusion criteria

- Cirrhosis at any time
- HBeAg to anti-HBe seroconversion within the last 3 years
- Interferon use in the last 3 years
- Contraindications to interferon use
- Participation in HBV-specific therapeutic vaccine studies within 12 months
- HCV, HDV or HIV co-infection
- Immunosuppressant use
- Contraindications to interferon use including:

- The presence of, or history of severe psychiatric condition, particularly severe depression, suicidal ideation or suicidal attempt
- Presence of or history of psoriasis
- Platelet count < 90000/mm³
- Absolute Neutrophil count < 1500/mm³
- Uncontrolled thyroid function
- Pregnancy or breastfeeding
- Women of child-bearing potential not using an effective method of contraception
- Men not using an effective method of contraception
- Clinically significant comorbidities that, in the opinion of the investigator, render the patient unsuitable.

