5.4 Treatment

In the interferon arm patients will commence treatment four weeks after nucleos(t)ide analogue withdrawal with pegylated interferon α 2a 180 mcg s.c once weekly for 16 weeks. The first injection will be administered in the clinic supervised by an experienced research nurse or clinical nurse specialist.

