5.5 Follow-up

In the control arm visits 3-6 will be used to monitor safety. In the Interferon arm visits 4 - 8 will be used to monitor and manage the side effects of interferon therapy.

Biological samples will be taken according to the relevant visit schedule in Section 5.3.

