6 TREATMENTS

Patients in the Interferon arm (and alternative protocol interferon arms) will receive Pegylated interferon $\alpha 2a$ 180 mcg once weekly by subcutaneous injection. This is an open label study using a licensed medication in a licensed indication. Therefore the Peg-IFN will be issued on a standard hospital prescription and dispensed from standard pharmacy stock. No special labelling or packaging will be required. Storage and dispensing will be according to normal pharmacy protocols.

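### Section 6.3 prints all four peg-interferon dose-modification limits per ml where per litre is meant (a factor of 1000), and the platelet reduction limit needs a one-line clarification against the entry limit

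*Protocol*

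**What the plan says.** Protocol section 6.3 has two rules. Below 1 x10^9/ml for neutrophils or 100 x10^9/ml for platelets, "the dose of Peg-IFN will be reduced to 90 mcg / week". Below 0.5 x10^9/ml for neutrophils, or when "the platelet count falls below 50 10^9 /ml then Peg-IFN will be discontinued until the counts recover", the drug is interrupted.

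Section 4.1 (ii) lists, among the contraindications to interferon, "Platelet count < 90000/mm" and "Absolute Neutrophil count < 1500/mm" (both per cubic millimetre).

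Section 5.4 gives every interferon-arm patient "180 mcg s.c once weekly for 16 weeks", and section 6 repeats "180 mcg once weekly by subcutaneous injection". Neither gives a different starting dose for patients with low counts.

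In the interferon schedule of section 5.3, full blood counts fall at screening, at gap week 4 (when interferon starts) and at IFN weeks 2, 4, 8, 12 and 16. Section 5.5 says that visits 4 to 8 in this arm "will be used to monitor and manage the side effects of interferon therapy".

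**The concern.** The limits in section 6.3 and those in section 4.1 describe the same two blood counts in the same patients, so they should lie on the same scale. As printed they do not. These are the only numerical reduction and interruption limits that the protocol gives for its investigational drug, and no other section states them in the right unit.

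A second, smaller question appears once the unit is put right. One would expect the limits to descend from entry to reduction to stopping. For platelets, the reduction limit is higher than the entry limit. Some patients can therefore enter the trial, start the full dose and already be below the count at which section 6.3 lowers it.

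**Working it through.** **Inputs.** Section 6.3: reduce at neutrophils 1 or platelets 100; stop at neutrophils 0.5 or platelets 50, all printed as 10^9/ml. Section 4.1 (ii): entry requires neutrophils of at least 1,500/mm3 and platelets of at least 90,000/mm3.

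**Conversion.** 1 ml = 1,000 mm3 and 1 L = 1,000,000 mm3. A limit of x times 10^9/ml is therefore x times 1,000,000/mm3, and a limit of x times 10^9/L is x times 1,000/mm3.

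| Limit | Printed value | As printed (per ml), in /mm3 | If per litre, in /mm3 | Entry limit, /mm3 |
|---|---|---|---|---|
| Neutrophils, reduce | 1 | 1,000,000 | 1,000 | 1,500 |
| Neutrophils, stop | 0.5 | 500,000 | 500 | 1,500 |
| Platelets, reduce | 100 | 100,000,000 | 100,000 | 90,000 |
| Platelets, stop | 50 | 50,000,000 | 50,000 | 90,000 |

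**Literal reading.** Either count alone triggers the stopping rule. To avoid it as printed, a patient would need at least 500,000 neutrophils and 50,000,000 platelets per mm3. On the assumption that no eligible patient has counts of that order, everyone would meet the stopping rule before the first injection. Read per litre, all four values fall on the scale of the entry limits.

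**Order of the limits per litre.** The entry limits become 1,500 x 10^6 / 10^9 = 1.5 x10^9/L for neutrophils and 90,000 x 10^6 / 10^9 = 90 x10^9/L for platelets.

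- Neutrophils: entry 1.5, reduce 1.0, stop 0.5. These descend; entry minus reduction = 1.5 - 1.0 = +0.5.
- Platelets: entry 90, reduce 100, stop 50. Entry minus reduction = 90 - 100 = -10, so the two limits overlap for counts of 90-99.

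**Patients in the overlap.** A patient who enters with platelets of 95 x10^9/L starts at 180 mcg, because sections 5.4 and 6 give one starting dose. Suppose the count stays at 95 on treatment. If section 6.3 is a threshold applied at each count, the dose goes to 90 mcg. If its title, "Dose Modifications for Toxicity", is taken to mean that a drug-related drop is required, a stable 95 does not trigger it. If instead the count goes from 95 to 91 because of the drug, both readings lead to reduction. The doubt is therefore confined to patients who enter at 90-99 and show no clear drop on treatment.

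**The case against.** **On the unit.** The printed rule cannot be followed, since it would stop the drug in every patient before it started. The error therefore announces itself. Section 5 describes the centres as experienced with peg-interferon, and sections 6 and 9.1.2 have it prescribed from ordinary licensed stock. All of this stands and makes misuse implausible, but none of it corrects the text. A fault in reading the PDF is unlikely: the unit appears four times in the same form, while the bilirubin limit in section 6.5 comes through per litre.

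A reader might infer that patients could be overexposed. The documents do not support that. The literal error would withhold drug, and the platelet overlap leans towards earlier reduction.

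**On the platelets.** A reader might infer that the two platelet limits contradict each other, or that patients at 90-99 have no defined starting dose. Neither holds. One limit governs admission and the other governs dosing on treatment, and the starting dose is fixed at 180 mcg. The natural reading of section 6.3 is a threshold at each on-treatment count, which gives an answer for every patient. What remains is that the protocol does not say whether the sponsor intends that answer for patients who were below 100 from the outset. Moving either limit would be a clinical decision that the documents cannot settle.

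A reader might also try to turn earlier reduction into a loss of total interferon dose. The protocol gives neither the number of patients at 90-99 nor a rule for returning from 90 to 180 mcg, so such figures would rest on assumptions. With cirrhosis excluded, the number is probably small.

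**Conclusion.** The unit in section 6.3 is wrong by a factor of 1000 in all four limits. This follows from the protocol's own entry limits and needs no outside source. The practical risk is low, on the assumption that experienced prescribers read the limits per litre.

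The 10 x10^9/L platelet overlap is a fact of the text after correction, but it calls only for a clarifying note.

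The trial's inference is untouched. The sample size rests on HBsAg loss of 40% against 20%. The intention-to-treat population is everyone randomised. Per-protocol membership asks for at least 8 weeks of interferon without specifying a dose. The point is minor; it merits correction because it concerns a safety rule and costs almost nothing.

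**What to change.** Replace /ml with /L for all four limits in section 6.3.

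In the same section, add one sentence, worded by the sponsor's clinicians, confirming whether any on-treatment platelet count below 100 x10^9/L requires 90 mcg in patients who entered at 90-99 x10^9/L.

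Both changes can go into the next amendment with a short notice to sites. They change neither sample size nor analysis.

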6.4 Hepatitis Flare

A hepatitis flare is defined as an ALT greater than twice the upper limit of normal (ALT> 2 X ULN). If a patient reaches this level at any visit they will be asked to return for an unscheduled visit at which further blood tests will be taken. If the patient continues to meet the criteria for a flare they will continue to be seen at unscheduled visits until the flare has resolved (at which point they will return to the routine visit schedule) or if the flare worsens and meets the definition of an exaggerated flare they will recommence nucleos(t)ide analogues as described below.

6.5 Discontinuation of Study Treatment and Withdrawal from Study

(i) Recommencement of nucleos(t)ide analogues

Retreatment with nucleos(t)ide analogue therapy will be recommenced according to the following criteria for exaggerated flares:

- 1. Disturbance of liver synthetic function
 - a. Bilirubin > 35 uMol/l
 - b. INR > 1.3
- 2. ALT > 20 x upper limit of normal
- 3. If HBV DNA and/or ALT remain persistently elevated for more than 6 months
- 4. If, in the opinion of investigator or patient there is a risk to health

It is possible that there may be variation in the criteria used to determine whether a patient with hepatitis flare post cessation would need to be restarted on treatment according to criteria number 4. Data will be collected on patients considered for retreatment to determine whether any systematic differences appear between the two groups.

Recommencement will not be considered as a withdrawal from the study. A form will be completed in the eCRF to document the date and reason for recommencement. Patients who resume nucleos(t)ide analogue therapy will be monitored at intervals at unscheduled visits until ALT, Bilirubin and INR test results begin to normalise and once they have returned to normal then the patients will return to the study visit schedule until the end of the study.

(ii) Permanent discontinuation of study treatment

Subjects may discontinue study medication for the following reasons:

- At the request of the subject.
- Adverse event/ Serious Adverse Event
- Allergic reaction to IMP
- In the event of pregnancy
- If the investigator considers that a subject's health will be compromised due to adverse events or concomitant illness that develops after entering the study.

(iii) Withdrawal from Study

Withdrawal from the study refers to discontinuation of study treatment and study procedures and can occur for the following reasons:

- Subject decision
- Loss to follow-up

In this situation the patient will be encouraged, where possible, to resume the nucleos(t)ide analogue treatment which they were taking before enrolling in the study.

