2.4 Secondary Endpoints

Efficacy endpoints

- The proportion of patients who achieve HBsAg loss who also have undetectable HBV DNA
- The proportion of patients in each group who become inactive HBV carriers; ie achieve a sustained virological response (HBV DNA < 2000 IU/mI & normal ALT values) at 3 years after randomisation
- Magnitude of reduction in quantitative HBsAg levels at 1, 6, 12, 24 & 36 months after randomisation
- Magnitude of changes in antiviral T cells response at 1, 5, 6, 12, 24 & 36 months after randomisation
- Magnitude of changes in NK cells response at 1, 5, 6, 12, 24 & 36 months after randomisation

Safety endpoints

• Proportion of patients in each group with exaggerated hepatitis flares

- Proportion of patients resuming nucleos(t)ide analogue therapy
- Adherence to pegylated interferon therapy

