An SAE form should be completed and entered into the eCRF for all SAEs within 24 hours. This will automatically send alert emails to the Chief Investigator, the Project Manager and the Sponsor.

Safety Reporting Overview

* Unless identified in the protocol as not requiring immediate reporting

Contact details for reporting SAEs and SUSARs

Follow the study specific procedure for reporting SAEs and SUSARs and complete an SAE form & submit to the Study Coordination Centre as soon as possible (within 24 hrs). SAE forms are available on the InForm eCRF system.

E-mail: [contact]

(iii) Definition of an Adverse Reaction (AR)

All untoward and unintended responses to an IMP related to any dose administered or relating to the withdrawal of the patient from nucleos(t)ides. All AEs judged by either the reporting investigator or the sponsor as having reasonable causal relationship to a medicinal product qualify as adverse reactions. The expression reasonable causal relationship means to convey in general that there is evidence or argument to suggest a causal relationship.

Exaggerated hepatitis flares are defined according to the following criteria:

- 1. Disturbance of liver synthetic function
 - a. Bilirubin > 35 uMol/l
 - b. INR > 1.3
- 2. ALT > 20 x upper limit of normal

- 3. If HBV DNA and/or ALT remain persistently elevated for more than 6 months
- 4. If, in the opinion of investigator or patient there is a risk to health

These are an expected reaction to nucleos(t)ide withdrawal and will not be recorded or reported as an AR/AE. Exaggerated flares will be recorded in the Case Report Form to monitor patient safety throughout the trial as described elsewhere in the protocol.

Expected non-serious side effects of interferon (as documented in the SMPC) will not be recorded as adverse reactions.

(iv) Definition of a Serious Adverse Reaction (SAR)

A SAR is defined as a SAE that is judged to be related to any dose of study drug administered to the subject or withdrawn from the subject.

(v) Definition of Suspected Unexpected Serious Adverse Reaction (SUSAR)

Any SAR that is NOT consistent with the applicable product information as set out in the Investigator Brochure (IB) or Summary of Product Characteristics (SPC) ie is unexpected.

An unexpected reaction to nucleos(t)ide withdrawal is defined as one which has temporal or biological relationship to the intervention but does not include a hepatitis flare.

(vi) Reporting of SUSARs

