8.2 Data Analysis

(i) Primary Endpoint Analysis

This analysis will be performed primarily on an intention to treat (ITT) basis. The ITT population will be all subjects who have been randomized. Secondarily, a per protocol analysis will be performed. The per protocol population will be those confirmed to be eligible who have not resumed nucleos(t)ide analogues for patient/ physician preference and those, in the interferon arm, who have completed at least 8 weeks of interferon therapy. Rates of HBsAg loss will be compared between the two groups using logistic regression adjusting for the stratification factors HBsAg titre and centre. Results will be presented as odds ratios and their 95% confidence intervals.

(ii) Secondary outcomes

Secondary outcomes to be compared between the two groups will include the primary outcome assessed at one year and at two years from baseline. Kaplan-Meier plots will be produced to show the persistence of HBsAg. The plots will be supported by formal secondary analyses using Cox proportional hazards model methods

Achievement of the inactive carrier state (defined above) will be analysed using the same procedures as the primary outcome. A statistical analysis plan will be developed and approved by the Trial Steering committee prior to any regular analysis for reports to the Data Monitoring Committee. This plan will include details of the statistical methods to be used to analyse the outcomes, and describe the methods to undertake sensitivity analyses for handling missing data. The plan will contain conform with the Clinical Trials Unit standard operating procedures

(iii) Predictors of HBsAg Loss

Predictive factors for HBsAg loss will be explored using univariate and multivariate logistic regression analysis. Separate models will be fitted for the following variables: gender, age, duration of antiviral therapy, viral genotype, viral load pre-treatment, HBsAg titre, centre, peak ALT value post withdrawal, peak viral load post withdrawal, hepatic cccDNA, number of infected hepatocytes and ELISPOT counts. Odds ratios and their 95% confidence intervals produced from each of the models will be presented. Following this, a multivariate logistic regression analysis will be performed will include the variables that were statistically significant in the univariate analysis plus a variable for treatment group.

(iv) Safety analysis

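### The exaggerated-flare safety endpoint uses the same four-item list as the restart criteria, including an open-label opinion item, so its comparison between arms can be biased by willingness to restart treatment

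*Protocol*

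**What the plan says.** Section 2.4 lists two separate safety endpoints: "Proportion of patients in each group with exaggerated hepatitis flares", and the proportion resuming nucleos(t)ide analogues.

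Section 6.4 sets the ordinary flare: "A hepatitis flare is defined as an ALT greater than twice the upper limit of normal". It treats the exaggerated flare as a worse stage of that event: "if the flare worsens and meets the definition of an exaggerated flare they will recommence nucleos(t)ide analogues".

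Section 6.5(i) gives the list, introduced by "Retreatment with nucleos(t)ide analogue therapy will be recommenced according to the following criteria for exaggerated flares". Section 7.4(iii) gives the same four items under "Exaggerated hepatitis flares are defined according to the following criteria". They are:

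1. disturbed liver synthetic function (bilirubin > 35 µmol/l, INR > 1.3);
2. ALT > 20 × ULN;
3. a persistence item, worded "If HBV DNA and/or ALT remain persistently elevated for more than 6 months";
4. an opinion item with no laboratory condition, worded "If, in the opinion of investigator or patient there is a risk to health".

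Section 6.5(i) accepts that use of item 4 may vary. It plans to collect data to see whether the arms differ systematically, and records the date and reason of each restart on the eCRF. Section 5 states that the trial is open label and that up to 45% of patients may need retreatment. Section 3.1 bases the 40% and 60% pilot rules on exaggerated flares, and section 8.2(iv) sends flare counts by arm to the Data Monitoring Committee.

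**The concern.** One list does two jobs. It tells the clinician when to restart treatment, and it defines the outcome used to judge hepatic safety. A restart rule can reasonably include judgement. An outcome compared between unblinded arms should not depend on it, because a more cautious attitude in one arm then appears as more flares in that arm.

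The endpoint also carries much of the safety comparison. Under section 7.3, abnormal liver tests and HBV DNA are not recorded as adverse events, and under section 7.4(iii) exaggerated flares are not recorded as adverse reactions or events. Apart from SAEs, this endpoint is the main comparative measure of hepatic safety for secondary objectives 1 and 2. It also decides whether a pilot arm is discontinued or the trial stopped.

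**Working it through.** **1. The sections side by side.**

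- Items 1 and 2 are numerical laboratory limits.
- Item 3 joins HBV DNA and ALT by and/or, and gives no level for elevated. HBV DNA alone can satisfy it.
- Item 4 needs no laboratory value.
- Section 6.4 requires a flare (ALT > 2 × ULN) that worsens. The list in 7.4(iii) stands alone with no such condition. In 6.5(i) the list also has no condition, although the commentary on item 4 speaks of a patient with a flare.

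Take a patient with normal ALT whose HBV DNA is judged elevated for more than six months. Under 6.4 this patient has no flare at all. Under 7.4(iii) the same patient has an exaggerated flare.

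The cross-references add to this. Section 3.1 points to section 6.4(i) and section 8.2(iv) to section 6.4 for the definition, but the list stands in 6.5(i) and 7.4(iii).

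**2. Overlap of the two endpoints.** Every restart made under the list is an exaggerated flare by definition. The endpoints separate only where a patient meets an item but does not restart, or restarts for a reason outside the list, such as pregnancy (7.4(viii)). They therefore largely coincide.

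**3. Link to the pilot rule.** The protocol states no expected rate or power for flares, so there is no plan figure to reproduce. The figures that bear on the point are:

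- expected retreatment, up to 45% (section 5), which is 0.45 × 120 = 54 patients per arm;
- the arm rule, more than 40% (section 3.1);
- 25 pilot patients per arm (Table 1).

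More than 40% of 25 means 11 or more. The chance of meeting the rule in one arm is P(X ≥ 11) for X ~ Binomial(25, p):

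| True rate p | Chance that one arm exceeds 40% |
|---|---|
| 20% | 0.6% |
| 30% | 9.8% |
| 40% | 41% |
| 45% | 62% |

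At 45% in both arms, the chance that at least one arm exceeds the limit is 1 − (1 − 0.616)² ≈ 85%. The 62% and 85% are upper figures. The 45% is an upper bound with no time frame, and the pilot assessment comes after the four-week gap and two months of interferon, about three months on study. Item 3 needs more than six months, so it can add few events by then. Item 4 is the main discretionary route in the pilot.

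**4. What a difference in judgement could do.** All rates here are assumptions. Let o be the laboratory-defined rate, equal in both arms, and q the share of the remaining patients counted through item 4 alone. The observed rate is o + (1 − o) × q. The last column is the chance of a significant result in a two-sided 5% comparison of proportions with 120 per arm. The protocol names no test for flares.

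| o | q in the two arms | Observed rates | Chance of significance |
|---|---|---|---|
| 20% | 10%, 10% | 28%, 28% | 5% |
| 20% | 0%, 10% | 20%, 28% | 0.305 |
| 20% | 5%, 20% | 24%, 36% | 0.528 |
| 20% | 0%, 20% | 20%, 36% | 0.792 |
| 30% | 0%, 20% | 30%, 44% | 0.614 |

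Equal use of item 4 raises both rates but creates no false difference. Unequal use does. In the last row, the chance that the arm with the additions meets the pilot rule rises from 9.8% (true rate 30%) to 58% (44%).

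**The case against.** The strongest defence is that the core of the composite is objective. Bilirubin, INR and ALT > 20 × ULN are numerical, and liver tests and prothrombin time are scheduled at every visit in every arm. SAEs are recorded throughout, restart reasons are captured, and the protocol itself plans to look for differences in the use of item 4. The objectives only explore safety, and analysis detail is left to a statistical analysis plan that is not shown. All of this stands. A reader might infer that the endpoint does not measure flares, or that objectives 1 and 2 cannot be answered. The documents do not support that.

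Three further inferences also go too far:

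- **A simple request to restart counts as a flare.** Item 4 requires a perceived risk to health, and section 8.2(i) names preference separately: "who have not resumed nucleos(t)ide analogues for patient/ physician preference". The boundary between a patient's view of risk and a patient's preference is not drawn, but that does not make them the same.
- **An inactive carrier is also an exaggerated flare.** This holds only if HBV DNA below 2000 IU/ml counts as elevated, which the protocol does not say.
- **A raised INR from anticoagulation counts.** INR sits under disturbed liver synthetic function, which argues against it.

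It is also fair that a laboratory-only endpoint is not free of the problem, since an early discretionary restart may stop a flare before it reaches a laboratory limit.

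What the defence does not remove is the definition itself. Looking for differences in the use of item 4 does not take those events out of the endpoint, and it is the protocol that fixes the definition and the pilot rules.

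**Conclusion.** The point holds in a limited form. The exaggerated-flare endpoint mixes laboratory-defined flares with discretionary or DNA-only restarts and largely duplicates the resumption endpoint. Its between-arm comparison, the DMEC reports and the pilot rules can therefore be biased by differing willingness to restart. Section 6.4 also conflicts with the free-standing lists, and two cross-references point to the wrong section.

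The size of the bias is unknown. The protocol gives no split of restarts by item and no reason to expect a particular imbalance, so the table of assumed rates shows what is possible and is not a forecast. The comparison of 45% with 40% shows only that the expected upper level of retreatment lies above a threshold measured with the same list. It does not show that the pilot will trigger.

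The primary endpoint, a laboratory HBsAg result, is not defined by this list.

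**What to change.** Leave the clinical restart criteria unchanged. The sponsor should reconcile sections 6.4, 6.5(i) and 7.4(iii), correct the references in 3.1 and 8.2(iv), and state which count the pilot thresholds use.

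For the between-arm analysis and DMEC reporting:

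- derive the flare endpoint from recorded laboratory values (items 1 and 2), by the same rule in both arms, whether or not treatment was restarted;
- show item 3 events separately, split into ALT-based and HBV DNA-only, so that prolonged ALT elevation stays visible;
- report opinion-only (item 4) restarts under resumption of treatment, by the recorded reason;
- keep the full four-item composite as a supporting summary.

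The cost is protocol wording and one extra table, as the laboratory values and restart reasons are already collected. The headline flare rate will be lower. Some bias remains: early discretionary restarts can prevent laboratory-defined flares, and the interferon schedule has visits at weeks 6, 20 and 42 that the control schedule lacks, so it has more chances to detect an event. Both summaries should therefore be shown together.
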